12.1.1 Efficacy analysis set

All analyses for the primary bleeding endpoint will be performed on the ITT and PP population. The primary analysis will be performed on the ITT population. This analysis will be repeated in the PP population to support the primary results.

The primary bleeding endpoint is the composite of BARC Types 2, 3 or 5 bleeding.

12.1.2 Safety analysis set

Analyses for the primary ischemic endpoint will be performed on the PP cohort. A secondary analysis for the primary ischemic endpoint will be performed in the ITT cohort.

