1.1 Research hypothesis

The overall hypothesis of the current study is that three months post-PCI of dual antiplatelet therapy with aspirin and ticagrelor, continued monotherapy with ticagrelor alone versus ticagrelor plus aspirin for an additional year will be superior with respect to bleeding and non-inferior with respect to ischemic events in high-risk patients undergoing elective or urgent PCI.

This hypothesis will be tested in the following two specific aims:

Aim 1: To determine the impact of ticagrelor alone versus ticagrelor plus aspirin in reducing clinically relevant bleeding among high-risk patients who had PCI.
	
Hypothesis 1: A DAPT strategy of ticagrelor + ASA for 3 months followed by ticagrelor alone for an additional 12 months will be superior to ticagrelor plus aspirin with respect to clinically relevant bleeding (BARC \geq 2) in high-risk patients undergoing PCI.

Aim 2: To determine the impact of ticagrelor alone versus ticagrelor plus aspirin in reducing ischemic adverse events at one year among high-risk patients undergoing PCI
	
Hypothesis 2: A DAPT strategy of ticagrelor + ASA for 3 months followed by ticagrelor alone for an additional 12 months will be non-inferior to ticagrelor plus aspirin for with respect to ischemic adverse events at 1 year in high-risk patients undergoing PCI.

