12.2 Methods of statistical analyses

Unless otherwise stated, all hypothesis tests will be performed using two-sided tests at the 5% significance level. Continuous variables will be summarized using descriptive statistics including means and standard deviations if normally distributed or median with interquartile ranges for skewed distributions. Discrete variables will be summarized using absolute and relative frequencies.

Demographic and baseline characteristics will be summarized by randomized treatment group and for all randomized subjects combined. Baseline characteristics that will define subgroups of interest for the efficacy and safety analyses are:

- Age group (< 65, >= 65 years)
- Race (Caucasian, non-Caucasian)
- Gender (Male, Female)
- Geographic Region (US, non-US)
- Diabetes Mellitus (yes, no)
- Chronic Kidney Disease (yes, no)

- CAD Presentation (Stable, Unstable)
- PCI Status (Elective, Urgent)
- Stent length implanted (< 30 mm, >=30 mm)
- BMI (above median, below median)
- History of Prior MI (yes, no)
- Multivessel disease (yes, no)

Censoring: Subjects not experiencing any endpoint will be censored at time of death, last contact date (for subjects who withdraw consent or are lost to follow-up) or 365 days after randomization, whichever comes first.

Analysis for the Primary Bleeding Endpoint: This analysis will be performed on the ITT population. The primary objective is to determine if ticagrelor monotherapy is superior to ticagrelor plus aspirin for the primary efficacy endpoint (BARC Types 2, 3 or 5 bleeding). The null hypothesis for this analysis is that the HR for the experimental group (H_0) = 1. The alternative hypothesis is that the HR for the experimental group (H_A) \neq 1. A test of superiority at the two-sided 0.05 level will be performed using a Cox proportional hazard model that includes treatment group as a covariate. A point estimate and two-sided 95% CI for the relative risk as measured by the hazard ratio will be calculated based on the Cox proportional hazards model. Event rates will be estimated at one year and Kaplan-Meier curves will be plotted for the time from randomization to the first occurrence of confirmed BARC Type 2, 3 or 5 bleeding by treatment group. This analysis will be repeated in the PP cohort to support the primary results.

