Analysis for the Primary Ischemic Endpoint: The analysis for the primary ischemic endpoint will be performed on the PP cohort. The primary objective is to determine if ticagrelor monotherapy is non-inferior to ticagrelor plus aspirin for the primary safety endpoint (all-cause death, non-fatal myocardial infarction, or stroke). A test of non-inferiority at the one-sided 0.025 level will be performed. Event rates will be estimated at one year and Kaplan-Meier curves will be plotted for the time from randomization to the first occurrence of confirmed all-cause death, non-fatal myocardial infarction, or stroke or by treatment group. Assuming an event rate of 8.0% in the control group, a sample size of 8200 will yield 80% to exclude a non-inferiority margin of 1.6%. If the upper limit of the 95% CI for the point estimate of the absolute risk difference is less than or equal to 1.6% then the criteria for non-inferiority will be met. This non-inferiority margin translates to a relative risk of 20% assuming the observed event rate equals 8.0% in the control arm.

Subgroup Analysis One year event rates for the primary efficacy and safety endpoints will be calculated in all subgroups described in section 12.2. Stratum-specific HRs and corresponding 95% CI will be calculated for each subgroup using a Cox proportional hazards

model. Formal interaction testing will be performed using the subgroup X treatment allocation as an additional term in the Cox model.

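### Ischemic non-inferiority is decided on the per-protocol set alone, so it can be claimed even when the randomised (ITT) comparison exceeds the 1.6-point limit

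*Combined protocol and SAP*

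**What the plan says.** - **Deciding population.** Section 12.1.2: "Analyses for the primary ischemic endpoint will be performed on the PP cohort". Section 12.2 repeats it: "The analysis for the primary ischemic endpoint will be performed on the PP cohort". The synopsis agrees.
- **Success rule.** The same paragraph of 12.2 sets the test ("A test of non-inferiority at the one-sided 0.025 level will be performed") and its criterion: "If the upper limit of the 95% CI for the point estimate of the absolute risk difference is less than or equal to 1.6" per cent, non-inferiority is met. No other criterion is given for this endpoint.
- **Role of ITT.** Section 12.1.2: "A secondary analysis for the primary ischemic endpoint will be performed in the ITT cohort". No limit is attached to it. Nothing asks for the two sets to agree or says what is concluded if they do not.
- **PP membership.** Section 12.1 removes patients who did not receive the allocated treatment and those who took under 80% of dispensed tablets (blinded drug or ticagrelor) by pill count. It makes no exception for tablets left over after a permitted stop.
- **Stopping drug.** Section 5.8 lists myocardial infarction, stent thrombosis and ischemic stroke among events after which the investigator may permanently stop study medication. Follow-up continues in all such randomised patients.
- **Bleeding.** Section 12.2: "This analysis will be performed on the ITT population". A PP repeat is planned as support.
- **Overall hypothesis.** Section 1.1 expects that monotherapy "will be superior with respect to bleeding and non-inferior with respect to ischemic events in high-risk patients".

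**The concern.** The set that decides the ischemic claim is formed by what happens after randomisation. A patient may have an infarction that counts towards the primary ischemic endpoint, stop study drug because of it, fall below 80% on the pill count, and so leave the only population that decides non-inferiority. If monotherapy caused more such events, it would also cause more such exclusions, and the PP difference would shrink towards non-inferiority. The ITT analysis would show this, but under the written rule it could not change the conclusion. The main reassurance that dropping aspirin costs little ischemic protection could then stand against the randomised comparison. Tightening individual PP definitions would not remove this, because any adherence-based set is formed after randomisation.

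**Working it through.** **Inputs from the documents.** "Assuming an event rate of 8.0% in the control group" (12.2); margin 1.6 points; one-sided 0.025; 8200 randomised; 4% cross-over or non-compliance (12.3, stated for the bleeding calculation).

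**Assumptions.** 1:1 allocation (4100 per arm), Wald intervals, and every PP exclusion share and event rate among excluded patients. The documents give no expected PP size.

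**1. The plan's own power figure.** With 8.0% in both arms, power = Φ(0.016/SE − 1.96), where SE = √(2 × 0.08 × 0.92/4100) = 0.00599. This is Φ(2.67 − 1.96) = 76.1%, against the stated 80%. The formula needs 4514 per arm (9028 in total) for 80%; 9000, the enrolled number, gives 79.9%. The shortfall is a separate matter, but it means the power needs restating anyway.

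**2. Can PP pass while ITT fails?** A constructed example:
- ITT: 350/4100 vs 328/4100. Difference 0.54 points, SE 0.608, upper limit 0.54 + 1.96 × 0.608 = 1.73. Fails.
- Exclude 246 per arm (6%), with 36 and 20 events among them. PP: 314/3854 vs 308/3854. Difference 0.16, SE 0.620, upper limit 1.37. Passes.

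Under the current text this trial claims non-inferiority.

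**3. How often, when the true ITT difference is exactly 1.6 points (8.0% vs 9.6%)?** 400,000 simulated trials per row. When the event rate among excluded patients is assumed, the PP rate in each arm is (overall rate − e × rate among excluded)/(1 − e), with e the excluded share. For example, with e = 10% and 12% vs 18%: control (0.080 − 0.012)/0.9 = 7.56%, experimental (0.096 − 0.018)/0.9 = 8.67%, difference 1.11 points.

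For event-driven exclusion, a fraction a of patients with an event and b of those without are removed, identically in both arms. The PP rate is p(1 − a)/[p(1 − a) + (1 − p)(1 − b)]. With a = 30% and b = 4% this is 5.96% vs 7.19%, difference 1.22 points.

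| Excluded patients (control vs experimental event rate) | Excluded | True PP difference | PP alone passes | Both pass |
|---|---|---|---|---|
| Unrelated to outcome | 4% | 1.60 | about 2.5% | 2.1% |
| Unrelated to outcome | 10% | 1.60 | 2.5% | 1.8% |
| 12% vs 12% | 4% | 1.67 | about 2% | 1.7% |
| 12% vs 12% | 10% | 1.78 | 1.3% | 1.1% |
| 12% vs 15% | 4% | 1.54 | 3.1% | 2.1% |
| 12% vs 15% | 10% | 1.44 | 4.3% | 2.0% |
| 12% vs 18% | 4% | 1.42 | 4.8% | 2.4% |
| 12% vs 18% | 10% | 1.11 | 11.8% | 2.5% |
| Event-driven, a = 10%, b = 6% | about 6% | 1.54 | 3.1% | 2.0% |
| Event-driven, a = 30%, b = 4% | about 6% | 1.22 | 9.9% | 2.2% |

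The last column does not depend on the assumptions in any important way. A trial that passes both sets has passed ITT, and ITT passes 2.5% of the time at a true difference of 1.6 points.

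**4. Power cost at 8200, 8.0% in both arms, exclusion unrelated to outcome.** The two test statistics are treated as bivariate normal with correlation √(PP share):
- 4% excluded: 74.4% for PP alone, 72.6% for both.
- 10% excluded: 71.7% for PP alone, 69.4% for both.

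**The case against.** Naming PP as primary for non-inferiority is a deliberate, consistently stated choice with a sound reason. Cross-over and non-adherence pull the arms together and can make non-inferiority easier to show in ITT, and section 5.8 allows open-label aspirin in place of blinded drug in some situations. This stands, and it is why PP should be kept, not replaced.

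A reader might infer three stronger things that the documents do not support.

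- **That PP necessarily inflates false claims.** It does not. Error stays at 2.5% if exclusion is unrelated to outcome, and PP is the stricter set if excluded patients are equally sicker in both arms (1.3% with 10% excluded). Bleeding-driven interruption could, on the trial's own hypothesis, fall more on the aspirin arm. More extreme assumptions give far larger figures (about 44% with 10% excluded and 8% vs 20% events among them), but nothing in the plan supports such inputs.
- **That benefit and harm are simply measured in different populations.** Bleeding is repeated in PP and ischemia is analysed in ITT, so both endpoints will be reported in both sets. What is missing is a decision rule, not an analysis.
- **That the plan contradicts itself.** It does not.

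Two further arguments have partial force. Blinding (5.4.1) means stopping decisions are made without knowing the arm. The event-driven rows use identical exclusion rules in both arms, however, and still give about 3–10%, because the arm with more events loses more of them. It can also be said that passing is correct for a PP estimand: in the 11.8% row the true PP difference is 1.11 points, inside the margin. That is so, and the error rates above are explicitly measured against the ITT difference.

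**Conclusion.** The point holds as a gap in the decision rule. Non-inferiority rests on PP alone, PP membership can be affected by endpoint events, and the planned ITT analysis cannot alter the claim even when its upper limit exceeds 1.6 points.

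The direction and size of any bias cannot be derived from the documents. Under the assumed exclusions, PP-alone false non-inferiority against the ITT difference runs from about 1% to about 12%, with 2.5% when exclusion is unrelated to outcome. At the plan's own 4% non-compliance figure the assumed event rates give about 2% to 4.8%. Requiring both sets holds it at or below 2.5% throughout. This is a cheap improvement to a defensible design, not the correction of an error.

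**What to change.** In 12.1.2, 12.2 and the synopsis, state that non-inferiority is claimed only if the upper limit of the two-sided 95% CI for the one-year risk difference is at most 1.6 points in both the PP and the ITT population. Restate the non-inferiority power for this joint rule at 8200 randomised, with the assumed PP share given.

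**Cost.** The wording changes, but no new data or analysis is needed: ITT is already planned and follow-up continues after discontinuation. Power falls by about 2 points if exclusion is unrelated to outcome. The loss is larger where PP alone is favourably shifted: with 8.0% in both arms, 10% excluded and 12% vs 15% events among them, power goes from about 89% to about 76%, part of which is the removal of that shift. For 80% joint power with 8.0% in both arms, about 9,990 (6% excluded) to 10,460 (10% excluded) would have to be randomised. PP alone would already need about 9028/0.94 = 9,605 to 9028/0.90 = 10,032, so most of the shortfall exists under the current rule.

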12.2 Methods of statistical analyses

Unless otherwise stated, all hypothesis tests will be performed using two-sided tests at the 5% significance level. Continuous variables will be summarized using descriptive statistics including means and standard deviations if normally distributed or median with interquartile ranges for skewed distributions. Discrete variables will be summarized using absolute and relative frequencies.

Demographic and baseline characteristics will be summarized by randomized treatment group and for all randomized subjects combined. Baseline characteristics that will define subgroups of interest for the efficacy and safety analyses are:

- Age group (< 65, >= 65 years)
- Race (Caucasian, non-Caucasian)
- Gender (Male, Female)
- Geographic Region (US, non-US)
- Diabetes Mellitus (yes, no)
- Chronic Kidney Disease (yes, no)

- CAD Presentation (Stable, Unstable)
- PCI Status (Elective, Urgent)
- Stent length implanted (< 30 mm, >=30 mm)
- BMI (above median, below median)
- History of Prior MI (yes, no)
- Multivessel disease (yes, no)

Censoring: Subjects not experiencing any endpoint will be censored at time of death, last contact date (for subjects who withdraw consent or are lost to follow-up) or 365 days after randomization, whichever comes first.

Analysis for the Primary Bleeding Endpoint: This analysis will be performed on the ITT population. The primary objective is to determine if ticagrelor monotherapy is superior to ticagrelor plus aspirin for the primary efficacy endpoint (BARC Types 2, 3 or 5 bleeding). The null hypothesis for this analysis is that the HR for the experimental group (H_0) = 1. The alternative hypothesis is that the HR for the experimental group (H_A) \neq 1. A test of superiority at the two-sided 0.05 level will be performed using a Cox proportional hazard model that includes treatment group as a covariate. A point estimate and two-sided 95% CI for the relative risk as measured by the hazard ratio will be calculated based on the Cox proportional hazards model. Event rates will be estimated at one year and Kaplan-Meier curves will be plotted for the time from randomization to the first occurrence of confirmed BARC Type 2, 3 or 5 bleeding by treatment group. This analysis will be repeated in the PP cohort to support the primary results.

Analysis for the Primary Ischemic Endpoint: The analysis for the primary ischemic endpoint will be performed on the PP cohort. The primary objective is to determine if ticagrelor monotherapy is non-inferior to ticagrelor plus aspirin for the primary safety endpoint (all-cause death, non-fatal myocardial infarction, or stroke). A test of non-inferiority at the one-sided 0.025 level will be performed. Event rates will be estimated at one year and Kaplan-Meier curves will be plotted for the time from randomization to the first occurrence of confirmed all-cause death, non-fatal myocardial infarction, or stroke or by treatment group. Assuming an event rate of 8.0% in the control group, a sample size of 8200 will yield 80% to exclude a non-inferiority margin of 1.6%. If the upper limit of the 95% CI for the point estimate of the absolute risk difference is less than or equal to 1.6% then the criteria for non-inferiority will be met. This non-inferiority margin translates to a relative risk of 20% assuming the observed event rate equals 8.0% in the control arm.

Subgroup Analysis One year event rates for the primary efficacy and safety endpoints will be calculated in all subgroups described in section 12.2. Stratum-specific HRs and corresponding 95% CI will be calculated for each subgroup using a Cox proportional hazards

model. Formal interaction testing will be performed using the subgroup X treatment allocation as an additional term in the Cox model.

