
Analysis for Primary Ischemic Endpoint
	
The analysis for the primary ischemic endpoint will be performed on the PP cohort. The primary objective is to determine if ticagrelor monotherapy is non-inferior to ticagrelor plus aspirin for the primary ischemic endpoint (all-cause death, non-fatal myocardial infarction, or stroke). Event rates will be estimated at one year and Kaplan-Meier curves will be plotted for the time from randomization to the first occurrence of confirmed all-cause death, non-fatal myocardial infarction, or stroke or by treatment group. A test of non-inferiority at the one-sided 0.025 level will be performed. . . . Assuming an event rate of 8.0% in the control group, a sample size of 8200 will yield 80% power to exclude an absolute non-inferiority margin of 1.6%. If the upper limit of the 95% CI for the point estimate of the absolute risk difference between groups is less than or equal to 1.6% then the criteria for non-inferiority will be met. This non-inferiority margin translates to a relative risk of 20% assuming the observed event rate equals 8.0% in the control arm.

Statistical Methods
	
Unless otherwise stated, all hypothesis tests will be performed using two-sided tests at the 5% significance level. Continuous variables will be summarized using descriptive statistics including means and standard deviations if normally distributed or median with interquartile ranges for skewed distributions. Discrete variables will be summarized using absolute and relative frequencies.

Sample Size Parameters
	
A cumulative bleeding rate of 4.5% is anticipated between time of randomization and 1 year. Assuming a 2% loss to follow-up and non-compliance / cross-over rate of 4%, the current trial will require 8200 subjects to detect a relative reduction in bleeding of 28% with ticagrelor monotherapy with 80% power and a Type I error of 0.05. It is anticipated that approximately 8% - 10% of enrolled subjects will not be eligible for randomization and therefore 9000 subjects will be enrolled at the time of PCI.

[figure not shown]

TABLE OF CONTENTS	PAGE
TITLE PAGE	1
PROTOCOL SYNOPSIS	2
TABLE OF CONTENTS	7
PROTOCOL SIGNATURE PAGE	11
LIST OF ABBREVIATIONS	12
1. INTRODUCTION	13
1.1 Research hypothesis.....	14
1.2 Rationale for conducting this study	14
1.3 Benefit/risk and ethical assessment.....	15
2. STUDY OBJECTIVES	15
2.1 Primary objective	15
2.2 Secondary objective	16
2.3 Exploratory objectives	16

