12.1 Description of analysis sets

The Enrolled Population consists of all subjects who signed informed consent.

The intention-to-treat (ITT) population will consist of all subjects who have been randomized (i.e. when the subject number and allocated treatment are recorded in the EDC). Subjects will be analyzed in the treatment group assigned by the EDC.

The per-protocol population (PP) will consist of all randomized subjects without any major deviations from the protocol. The following deviations will lead to exclusion from the PP population

- Subjects not receiving the assigned treatment as allocated by the EDC or no treatment at all
- Non-compliance to study drug (aspirin or placebo) or ticagrelor. Non-compliance is defined as taking less than 80% of dispensed tablets based on manual pill bottle count at each study visit.

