12.3 Determination of sample size

Power calculations are based on a superiority comparison for the primary efficacy endpoint of clinically relevant bleeding (BARC Types 2, 3 or 5) at 1 year from randomization (15 months after enrollment). Based on bleeding rates as shown in Table 3, a cumulative bleeding rate of 4.5% is anticipated between time of randomization and 1 year. This estimate is more conservative than rates shown in Table 3 as subjects sustaining a major hemorrhagic event in the first 3 months after PCI will not be randomized. Assuming a 2% loss to follow-up and non-compliance / cross-over rate of 4%, the current trial will require 8200 subjects to detect a relative reduction in bleeding of 28% with ticagrelor monotherapy with 80% power with a Type I error of 0.05. It is anticipated that approximately 8% - 10% of enrolled subjects will not be eligible for randomization and therefore 9000 subjects will be enrolled. Additional sample size estimates are provided in Table 4 assuming different control bleeding rates and risk reductions. References for the sample size estimates include Lakatos 1988, Biometrics volume 44 pages 229-241; and Lakatos 2002, Statistics in Medicine, Volume 21 pages 1969-1989.

Assuming a 1 year ischemic adverse event rate of 8% the current study will have 80% power to exclude a non-inferiority margin of 1.6% (upper limit of 95% CI for absolute risk difference).

Table 2 Bleeding Rates/Effect Sizes for Primary Endpoint Power Calculations

Basis for Proposed Bleeding Event Rates in TWILIGHT Power Calculations			
Study	Study Type	Time Point	BARC \geq 2 Rate
DAPT	RCT	18 months	~ 4.2%
PARIS (unpublished data)	Registry		
Age > 65	Registry	1 year	8.6%
Diabetes Mellitus (on insulin)	Registry	1 year	8.3%
Diabetes Mellitus (orals)			6.3%
Renal disease	Registry	1 year	13.2%
Vranckx et al., EHJ 2013	Post-hoc (TRACER)	500 days	14%
ADAPT-DES			
CrCl < 60 (Baber et al, TCT 2013)	Registry	1 year	10.0%
Rao et al., JACC Int 2013	NCDR CathPCI	In-hospital (women)	8.5%
Basis for Proposed Effect Size in TWILIGHT Power Calculations			

Study	Study Type	Comparators	Relative Bleeding Increase
Baigent et al., Lancet 2009	Pooled Data from Randomized trials	ASA vs. placebo/control	50% (1° prevention) 170% (2° prevention)
WOEST, Lancet 2013	RCT	ASA vs. placebo	~ 60%
CAPRIE, Lancet 1996	RCT	ASA vs. clopidogrel	~35% (GI hemorrhage)
Physician Health Study, NEJM 1989	RCT	ASA vs. Placebo	~35%

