De Berardis et al., JAMA 2012	Cohort study	ASA vs. No ASA	55%
Seshasai et al., Archives Int Med 2012	Meta-analysis of 9 RCTs	ASA vs. Placebo	~31%
HOT Trial, Lancet 1998	RCT	ASA vs. Placebo	~ 80%

Table 3 Power and Sample Size Scenarios for Primary Superiority Endpoint of BARC ≥ 2 Bleeding

Control Bleeding Rate	Relative Risk Reduction	Total Randomized Sample Size	Total Sample Size (Enrolled + Randomized) with 8% loss after enrollment*	Total Sample Size (Enrolled + Randomized) with 10% loss after enrollment*
5%	30%	6400	7000	7111
5%	28%	7400	8040	8222
5%	26%	8030	9800	10000
4.5%	30%	7090	7706	7900
4.5%	28%	8200	8913	9111
4.5%	26%	9700	10500	10800
4.0%	30%	8000	8700	8888
4.0%	28%	9300	10100	10333
4.0%	26%	10900	11800	12111

We anticipate that ~10% of enrolled subjects will not be eligible or lost for randomization. Power calculations assume 2% loss to follow-up and 4% cross-over/non-compliance.

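### The stated 80% power for ischemic non-inferiority does not reproduce: 8200 analysed patients give about 76%, and no allowance for per-protocol exclusions is given

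*Combined protocol and SAP*

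**What the plan says.** The power claim appears three times. Section 12.2 (Analysis for the Primary Ischemic Endpoint) says that "a sample size of 8200 will yield 80% to exclude a non-inferiority margin of 1.6" percentage points. The Synopsis has "a sample size of 8200 will yield 80% power to exclude an absolute non-inferiority margin of 1.6" percentage points. Both assume an 8.0% event rate in the control group. Section 12.3 says: "Assuming a 1 year ischemic adverse event rate of 8% the current study will have 80% power to exclude a non-inferiority margin of 1.6" percentage points, without assigning the rate to an arm.

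Section 12.2 fixes the test: "A test of non-inferiority at the one-sided 0.025 level will be performed". Non-inferiority is met if the upper 95% limit of the absolute risk difference does not exceed 1.6%.

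On the analysis set, section 12.1.2 says: "Analyses for the primary ischemic endpoint will be performed on the PP cohort". The ITT analysis of this endpoint is secondary. Under section 12.1, subjects leave the PP set if they did not receive the assigned treatment, took none, or were non-compliant: "Non-compliance is defined as taking less than 80% of dispensed tablets based on manual pill bottle count at each study visit".

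The number 8200 comes from the bleeding superiority calculation in section 12.3, where Table 3 lists it as the total randomized. The note to that table reads: "Power calculations assume 2% loss to follow-up and 4% cross-over/non-compliance".

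**The concern.** The stated inputs are enough to recompute the power, and the result is not 80%. The endpoint carries half of the trial's hypothesis (superior on bleeding, non-inferior on ischemic events). A reader of an inconclusive non-inferiority result would rely on this figure to judge how likely that result was if the regimens were truly equivalent.

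A second gap points the same way. The claim uses the full randomized number, but the test is run on a cohort from which some of those subjects are removed. The plan gives no expected size for that cohort, and its only loss and non-compliance figures belong to the bleeding endpoint.

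**Working it through.** **Inputs from the documents**

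- Control rate 8.0% (Synopsis, 12.2); a single 8% rate in 12.3.
- Margin 0.016 on the absolute risk difference (Synopsis, 12.2).
- One-sided alpha 0.025, so z = 1.960 (12.2).
- N = 8200 (Synopsis, 12.2).

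**Assumptions**

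- True rate of 8.0% in both arms, so the true difference is 0.
- 1:1 allocation, so 4100 per arm. The ratio is not stated in the readable text.

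**Step 1. The plan's own figure (stated: 80%)**

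- SE = sqrt(2 × 0.08 × 0.92 / 4100) = 0.005992
- z = 0.016 / 0.005992 − 1.960 = 0.710
- Power = Φ(0.710) = **76.1%**

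Simulating the plan's decision rule (upper 95% limit at or below 1.6%) over 2,000,000 trials also gives 76.1%.

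**Step 2. What 80% would need**

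- n per arm = (1.960 + 0.8416)² × 2 × 0.0736 / 0.016² = 4513.1, rounded up to 4,514, or **9,028 analysed** in total. This is 828 more than 8200, about 10%.
- With N held at 8200, the margin would have to be 2.8016 × 0.005992 = 1.68 points.

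**Step 3. Does another method recover 80%?** At 8200 and one-sided 0.025:

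| Method | Power |
|---|---|
| Farrington-Manning | 75.9% |
| Kaplan-Meier variance with 2% loss | 75.7% |
| Continuity correction | 74.8% |
| Null variance at 8.0% and 9.6% | 73.4% |
| Schoenfeld, margin as hazard ratio 1.21 | 68.6% to 72.7% |
| Freedman, same hazard ratio | 68.4% to 72.5% |

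All fall below 76.1%. One-sided 0.05 gives 84.7%, which does not match either. About 80% appears only with inputs the plan does not give for this test. Examples are the enrolled number of 9000 (79.9%), a superiority formula for 8.0% against 6.4% (80.0%), a common rate near 7.2%, or an experimental rate near 7.92%. Nothing in the documents shows which, if any, was used.

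**Step 4. Sensitivity to the two assumptions, at 8200**

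- Experimental rate 7.92%: 80.2%. Experimental rate 8.1%: 70.4%.
- Allocation 1.5:1: 74.4%. Allocation 2:1: 71.1%. So 1:1 is the favourable case.

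**Step 5. Effect of PP exclusions** (PP sizes are illustrations)

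| Excluded | Analysed | Power | Type II risk |
|---|---|---|---|
| 0% | 8200 | 76.1% | 23.9% |
| 4% | 7872 | 74.4% | 25.6% |
| 10% | 7380 | 71.7% | 28.3% |

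The 4% is borrowed from the bleeding calculation; the 10% has no source in the documents. The 2% loss to follow-up is not counted here, because it is not a PP exclusion. Section 12.2 censors those subjects at the "last contact date (for subjects who withdraw consent or are lost to follow-up").

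**The case against.** The strongest reply is that the decisive input is inferred. The Synopsis and section 12.2 fix the rate only for the control group, and no experimental-arm rate is given. The result is very sensitive to it: an advantage of about 0.08 points for monotherapy restores 80%. On this view the documents show that 80% does not reproduce under equal rates, not that it is wrong under every input. That limit on certainty stands. It does not remove the need for a correction. No lower experimental rate is stated anywhere, and section 12.3 quotes one 8% rate. Either the power is misstated or an essential input is missing.

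It can also be said that silence about the PP size does not prove that no allowance was made. That is fair as to what was done behind the scenes. But Table 3 labels 8200 as randomized, and even if all 8200 were analysed, power falls short of 80%. The PP percentages are illustrations and carry no weight beyond that. The missing design figure may state the allocation ratio, but no ratio improves on 1:1.

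Finally, this statement does not drive the sample size, and correcting it changes no design element or Type I error. That is true, and it is why the remedy is confined to wording. It does not make the stated power right.

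**Conclusion.** The concern holds. With 8.0% in both arms, 1:1 allocation and one-sided 0.025, 8200 analysed patients give 76.1% power to exclude a 1.6-point margin, 3.9 points short of the stated 80%. None of the non-inferiority methods tried on the stated inputs closes the gap. PP exclusions widen it by an amount the plan does not allow anyone to compute. The conclusion depends on equal true rates: an experimental rate of about 7.92% would support 80%, but the plan does not state one.

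**What to change.** Keep N and the 1.6% margin. In the Synopsis, section 12.2 and section 12.3, replace the power statement with wording such as:

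> *With 1:1 allocation and an 8.0% one-year event rate in both groups, 8200 analysed subjects give about 76% power to exclude an absolute margin of 1.6% (one-sided 0.025).*

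Add the power at the expected PP size and label that size as an assumption, for example about 74% if 4% of randomized subjects are excluded. If the 80% was derived from a lower experimental-arm rate, state that rate and the formula instead.

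The cost is wording in three places and one stated assumption. The declared power becomes slightly less favourable. No extra patients are needed, and alpha and the decision rule do not change.
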